**Response:**

**Faulty equipment and mass terminations of staff, for example.**

## **20.0      Withdrawal of Subjects**

**N/A:** This study is not enrolling subjects. This section does not apply.

20.1 *Describe anticipated circumstances under which subjects may be withdrawn from the research without their consent.*

**Response:** **If it is not in the best clinical interest of the participant or if the participant is unable to comply with study requirements, s/he will be withdrawn from the research, and notified of such withdrawal. This will be determined by the PI, investigators and coordinator.**

20.2 *Describe any procedures for orderly termination.*

*NOTE: Examples may include return of study drug, exit interview with clinician. Include whether additional follow up is recommended for safety reasons for physical or emotional health.*

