**Group A: Diabetic, Scaling & Root Planing (SRP) + Paroex® + Soft-Picks**

**Group B: Non-Diabetic, SRP + Paroex® + Soft-Picks**

**Group C: Diabetic, SRP**

**Group D: Non-Diabetic, SRP**

## 5.0 Local Number of Subjects

5.1 *Indicate the total number of subjects that will be enrolled or records that will be reviewed locally.*

Response: **104 with complete data; 26 per group**

5.2 *If applicable, indicate how many subjects you expect to screen to reach your target sample (i.e. your screen failure rate).*

Response: **250**

5.3 *Justify the feasibility of recruiting the proposed number of eligible subjects within the anticipated recruitment period. For example, how many potential subjects do you have access to? What percentage of those potential subjects do you need to recruit?*

Response: **We have a list of participants in previous studies that have given us permission to re-contact them about new studies. We also have a successful history of being able to make and surpass recruitment goals. Tactics such as word of mouth, flyers and posters, and ads have worked well in the past.**

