**Response: We estimate it will take 12-18 months to recruit and enroll 104 participants with complete data.**

*11.2 Describe the duration of an individual subject's participation in the study. Include length of study visits, and overall study follow-up time.*

**Response: Each participant's duration of participation is approximately 12-13 months, slightly longer if study visits are not completed as scheduled.**

*11.3 Describe the estimated duration for the investigators to complete this study (i.e. all data is collected and all analyses have been completed).*

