## 16.0 Provisions to Protect the Privacy Interests of Subjects

16.1 *Describe how you will protect subjects' privacy interests during the course of this research.*

*NOTE: Privacy refers to an individual's right to control access to him or herself. Privacy applies to the person. Confidentiality refers to how data collected about individuals for the research will be protected by the researcher from release. Confidentiality applies to the data.*

*Examples of appropriate responses include: "participant only meets with a study coordinator in a classroom setting where no one can overhear", or "the participant is reminded that they are free to refuse to answer any questions that they do not feel comfortable answering."*

Response:

Potential and enrolled participants will interact with the study staff, dentists, registered dental hygienists, dental assistants, laboratory technicians, research associates and data manager. Participants may choose not to answer questions, but if those questions provide critical information needed to answer the research questions, the person will not be allowed to remain in the study. When exams are performed, privacy is provided via individual examination rooms; when participants have samples such as saliva and plaque collected, they are provided privacy from the view of others; blood is collected and height and weight measured out of the view of others as well.

Participants are told they may withdraw from the study at any time with no adverse effects on them. They are told we need certain data and that data need is explained prior to enrollment (at the time of consenting).

16.2 *Indicate how the research team is permitted to access any sources of information about the subjects.*

*NOTE: Examples of appropriate responses include: school permission for review of records, consent of the subject, HIPAA waiver. This question does apply to records reviews.*

Response: **Consent of the participant.**

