**Response:**

**A minimum of 104 subjects will be enrolled in the study, with at least 26 participants per group. The study was powered to detect a difference in probing pocket depth (PPD) of 35% between groups, and a standard deviation (SD) of 0.5 for the distribution of 6 month changes. A sample size of 24 per group was estimated assuming approximately 80% power (alpha = 0.05). A minimum 26 subjects per group with an attrition rate of 10% will be enrolled in this study.**

**10-14-2021: We are continuing recruitment to greater than 100 participants in order to balance the numbers of participants per cell, to increase the size of the control group (no perio disease and no diabetes), and to increase the numbers with diabetes but no perio disease so that we have a more solid base on which to complete vigorous data analyses.**

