**Response:** **Inform the participant verbally and document in chart progress notes.**

20.3 *Describe procedures that will be followed when subjects withdraw from the research, including retention of already collected data, and partial withdrawal from procedures with continued data collection, as applicable.*

**Response:** **Participants will be asked if they wish to withdraw from all components of the study or if they will allow follow-up activities. For observational studies such as this one, withdrawal is not likely, but participants who want to withdraw will be asked if any samples already collected may be used in the research. If participant does NOT want those samples used, those samples will be destroyed.**

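### Withdrawal for non-compliance after randomisation, a target counted in completers and no as-randomised analysis leave the SPT-versus-SRP comparison open to selection bias

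*Combined protocol and SAP*

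**What the plan says.** **Withdrawal.** Section 10.1 randomises at the baseline visit, so any later removal is post-randomisation. Section 20.1, on withdrawal without the participant's consent, says: "if the participant is unable to comply with study requirements, s/he will be withdrawn from the research". The principal investigator, investigators and coordinator decide. No threshold or criterion is given. Section 4.1 calls the trial single-blind without saying who is blind. The rule covers all four groups.

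Section 16.1 adds that a participant who leaves critical questions unanswered "the person will not be allowed to remain in the study". This too applies to every group.

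**After withdrawal.** Section 20.3 says: "Participants will be asked if they wish to withdraw from all components of the study or if they will allow follow-up activities". It does not require the 6-month PPD examination. It also says "For observational studies such as this one, withdrawal is not likely", although section 4.1 describes a randomised controlled trial.

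**Target.** Section 5.1 gives "104 with complete data; 26 per group", and section 11.1 says "We estimate it will take 12-18 months to recruit and enroll 104 participants with complete data". Section 17.2 instead says "A minimum of 104 subjects will be enrolled in the study, with at least 26 participants per group", with 10% attrition.

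**Analysis.** Change in PPD at 6 months is the only primary endpoint (section 2.1). Section 17.1 deals mainly with the microbiome. It names no analysis set, missing-data method or primary PPD model.

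**The concern.** The first hypothesis in section 1.2 is that adding SPT improves clinical status more than SRP alone. Randomisation protects that comparison only if outcomes are sought in everyone randomised and analysed by allocated group. Here the team may remove participants on a ground that is probably prognostic: section 3.1 itself lists poor home care among the possible reasons for a poor response to SRP.

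The opportunity to fail is not the same in every group. Groups A and B must use and return home products; Groups C and D have none. If poor compliers leave mainly from A and B, the SPT participants who remain have a better prognosis than the SRP participants, and the estimated benefit is too large. A target counted in completers, with no analysis set defined, makes a completers' analysis the likely default.

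**Working it through.** **Inputs from section 17.2:** SD of 6-month change 0.5 (unit not stated, taken as mm); 24 per group for about 80% power; alpha 0.05 (taken as two-sided); 26 per group after allowing for 10% attrition.

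**Assumptions, not in the documents:** wS and wC, the shares of SPT and SRP participants withdrawn for non-compliance, and g, the amount by which those withdrawn would have responded worse than those retained.

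**1. The plan's own figure.** Section 17.2 says: "The study was powered to detect a difference in probing pocket depth (PPD) of 35% between groups". The base of the percentage is not given, so 24 per group cannot be derived forwards. Working back, the detectable difference is 0.5 × (1.960 + 0.842) × √(2/24) = 0.404 mm, or 0.413 mm by t-test. This serves only as a yardstick. (0.404 mm would be 35% of 0.404/0.35 = 1.15 mm.)

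**2. The two targets.**
- 104 randomised, 26 per group: 26 × 0.9 = 23.4 per group complete, just under the required 24. The inflation 24/0.9 = 26.7 rounds up to 27, not 26.
- 104 completers, 26 per group: 26/0.9 = 28.9, so 29 per group and 4 × 29 = 116 randomised.

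The two statements therefore differ by 116 − 104 = 12 randomised participants.

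**3. Bias of a completers' comparison.** If a share w of a group is withdrawn, its all-randomised mean is the retained mean minus w × g. The retained mean is therefore too favourable by w × g, and the bias in SPT minus SRP is g × (wS − wC).

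| wS | wC | g = 0.3 mm | g = 0.5 mm |
|---|---|---|---|
| 10% | 0% | +0.03 mm | +0.05 mm |
| 20% | 10% | +0.03 mm | +0.05 mm |
| 10% | 10% | 0 | 0 |
| 10% | 20% | −0.03 mm | −0.05 mm |

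The first row is 0.03/0.413 = 7% to 0.05/0.413 = 12% of the detectable difference. It spends the whole stated 10% attrition, in SPT, on non-compliance.

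**4. Type I error when SPT has no effect.** At 24 per group the standard error is 0.5 × √(2/24) = 0.144 mm. With a bias b, the two-sided rejection probability by normal approximation is Φ(b/0.144 − 1.96) + Φ(−b/0.144 − 1.96).
- b = 0.03 mm: b/SE = 0.21, giving 5.5%.
- b = 0.05 mm: b/SE = 0.35, giving 6.4%.

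If A and B are pooled against C and D (46.8 against 52 after 10% SPT withdrawal), the standard error is 0.5 × √(1/46.8 + 1/52) = 0.101 mm, and the same biases give 6.0% and 7.9%. The plan does not say which contrast is primary.

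**The case against.** The strongest reply is that the documents do not describe a completers' analysis. Nothing says that withdrawn participants are left out of the analysis or replaced. Section 17.2 counts 104 as enrolled, and section 20.3 leaves follow-up after withdrawal open. A reader might infer from sections 5.1 and 11.1 that compliers replace those removed, but that is inference, not plan. This part of the reply stands. It does not remove the point: the follow-up is optional, is not tied to the 6-month PPD examination, and no text says the data would be analysed as randomised.

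A reader might also infer that the bias must favour SPT. The documents do not support that.
- Section 20.1 refers to study requirements in general and sets no product-use threshold.
- The accounts of withdrawal and loss to follow-up in section 26.4 concern missed visits, which can occur in any group.
- The compliance questionnaire in section 10.1 goes to all subjects, so only product use and return are extra for Groups A and B. The section 16.1 rule also applies to all.
- The other ground in section 20.1, the participant's clinical interest, could remove more poor responders from SRP alone, which would reverse the sign.

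Finally, the plan calls itself a pilot with descriptive statistics. That weakens type I error as a yardstick, but the protocol also states a superiority hypothesis and a power calculation, lists formal tests, and intends the results to inform a larger study.

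**Conclusion.** The concern holds as an exposure to selection bias, not as a demonstrated bias. The plan allows removal after randomisation on a probably prognostic ground, counts its target in two incompatible ways, and does not secure an as-randomised comparison for its only primary endpoint. Bias towards SPT is plausible but unproven: equal withdrawal with an equal prognostic gap gives none, and heavier loss from SRP reverses it.

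At the stated 10% attrition the size is small: 0.03 to 0.05 mm and a two-sided type I error of about 5.5% to 6.4% at 24 per group. This assumes 10% withdrawal in SPT, none in SRP, and a gap of 0.3 to 0.5 mm. A reader might push this further. With 30% of SPT withdrawn, none of SRP, and a 0.5 mm gap (one full SD), the bias is 0.30 × 0.5 = 0.15 mm and type I error is about 17% by non-central t. Nothing in the documents supports withdrawal at three times the stated attrition, all in one arm. The change is still worth making, because it is cheap and the loss cannot be repaired at analysis.

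**What to change.** 1. **Section 20.1:** reword so that non-compliance alone does not end outcome follow-up. Seek the already scheduled PPD examinations, at least the 6-month one, in everyone randomised unless consent is withdrawn. Whether product use continues is left to the investigators.
2. **Section 17.1:** make the primary PPD comparison as randomised, using all available PPD data, with a sensitivity analysis for missing data. Report withdrawals by group and reason. Any compliers' analysis is secondary.
3. **Sections 5.1, 11.1 and 17.2:** state one target and say whether it counts participants randomised or completing. The aim is to restate the figure, not to enrol more.

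**Cost.** This is mainly protocol wording, since the visits are already planned. Some effort is needed to keep non-compliers attending, in a study that is now unfunded. The estimated effect may be slightly smaller than a compliers-only estimate. Outcomes of participants already withdrawn cannot be recovered, so those losses should be reported by group.

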**Response:** **Inform the participant verbally and document in chart progress notes.**

20.3 *Describe procedures that will be followed when subjects withdraw from the research, including retention of already collected data, and partial withdrawal from procedures with continued data collection, as applicable.*

**Response:** **Participants will be asked if they wish to withdraw from all components of the study or if they will allow follow-up activities. For observational studies such as this one, withdrawal is not likely, but participants who want to withdraw will be asked if any samples already collected may be used in the research. If participant does NOT want those samples used, those samples will be destroyed.**

## 21.0 Risks to Subjects

21.1 *List the reasonably foreseeable risks, discomforts, hazards, or inconveniences to the subjects related to their participation in the research. Consider physical, psychological, social, legal, and economic risks. Include a description of the probability, magnitude, duration, and reversibility of the risks.*

*NOTE: Breach of confidentiality is always a risk for identifiable subject data.*

**Response:** **None of the study procedures (e.g., oral health examination, periodontal measurements, collection of biological specimens) are considered experimental. They are all considered standard of care. Known possible risks of participating in this study are described below. As with all clinical procedures, this study may also involve unforeseen risks to participants.**

**Periodontal Examination:** The periodontal examination will involve procedures that are routine in dental practice. A licensed dentist or dental hygienist will perform the procedures. The risks from the periodontal examination include minor discomfort or pain during and

after the procedures and minor bleeding, inflammation, and swelling of the gums.

**Collection of Samples from the Mouth:** During the study, we will take samples of saliva and plaque. The saliva will be collected by having participants spit into a container. Both of these procedures have very little risk. Collecting plaque samples has a small risk of causing minor bleeding of the gums. This risk is low because all the examiners are experienced and skilled in proper collection technique.

**Blood Sample Collection:** Blood samples will be drawn by trained and experienced health care personnel. There may be some discomfort and bruising at the site where the needle enters the skin, and there is a very small risk of fainting. Infection in the area of needle insertion is rare.

**Vaginal Swab Sample Collection:** There is little risk to the participant in collecting vaginal swabs.

**Stool Collection:** There is little risk to the participant in collecting a stool sample. Specific instructions and supplies will be provided to minimize mess and unpleasantness.

**Dental radiographs:** About 18 radiographs will be taken. These x-rays will not be taken if suitable x-rays taken in the past two years are available to review, or if the dental clinician feels there is no clinical need for them. The amount of radiation exposure from the dental x-rays in this study is about 17.1 millirem (or 0.017 rem). This amount is below the 5 rem per year allowed for research participants by the National Institutes of Health (NIH) Radiation Safety Committee. The average person in the United States has a radiation exposure of about 0.36 rem per year from natural sources, such as the sun, outer space, and earth's air and soil. When taking x-rays, the lowest dose possible will be used and participants will wear a lead apron to reduce exposure.

Although there is no direct evidence that the amount of radiation exposure from participating in this study is harmful, there is indirect evidence that it may not be completely safe. There may be a very slightly increased risk of cancer.

Paroex® is a non-alcohol chlorhexidine preparation. With use of chlorhexidine, there is risk of reversible staining of teeth and the possibility of some alteration in taste. There is increased likelihood of staining in smokers, coffee drinkers and those who are susceptible to teeth staining in general. The cleaning of the front teeth that will be

**provided at the 3-month visit will help to reduce any staining that may occur. If there is any alteration in taste, it should go away when use of chlorhexidine stops. Paroex® was approved by the FDA November 29, 2005 (application # (ANDA) 076434).**

**Soft-Picks may cause some bleeding of the gums at first usage, but the bleeding should lessen and stop as use is continued (as gums heal). Soft-Picks are a readily available consumer product sold in supermarkets and drug stores. They are “510(k) exempt” from requiring FDA approval.**

**Taste Test: There is minimal risk to taking the Taste Test.**

*21.2 Describe procedures performed to lessen the probability or magnitude of risks, including procedures being performed to monitor subjects for safety.*

**Response: See above (21.1), well trained and experienced study staff, and below.**

**The electronic data files for study data do NOT include general identifiers except study Identification (ID) number. Examples of these files are Medical History file, Dental History file, medications file, blood testing results, periodontal examination data file where the results of the clinical examination are recorded and saved by ID number only. These files do not have names or other contact information though the medical history file does have date of birth (DOB). One study file has demographic information needed to identify participants and for communications and correspondence with the participants (names, address information, telephone numbers, email addresses). Another file has gender, ethnicity, age (up to 89 years), year of birth and the first three digits of the zip code by study ID number. Social security numbers are obtained for reimbursement purposes as required by Research Foundation, but are not included in data files. We do not collect insurance data, vehicle identifiers, device identifiers, URLs, IP address numbers, voice or finger prints, or photos of participants so they will not be included in the saved data files.**

*21.3 If applicable, indicate which procedures may have risks to the subjects that are currently unforeseeable.*

**Response: Unknown.**

*21.4 If applicable, indicate which research procedures may have risks to an embryo or fetus should the subject be or become pregnant.*

**Response: None known.**

*21.5 If applicable, describe risks to others who are not subjects.*

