## 8.0 Eligibility Screening

8.1 *Describe screening procedures for determining subjects' eligibility. Screening refers to determining if prospective participants meet inclusion and exclusion criteria.*

*Include all relevant screening documents with your submission (e.g. screening protocol, script, questionnaire)*

Response: Potential participants may respond to flyers, posters, advertisements or word-of-mouth by phone call. First, they will be screened over the phone and if eligible, scheduled for a screening visit which may be the same day as the first study visit (Baseline Visit (if eligible)). A script will be used for the screening phone call plus a screening checklist. In the screening telephone conversation, women are asked if they are pregnant and are ineligible for the Screening Visit if they say yes. At the Screening visit, women of childbearing age are given a pregnancy test and if positive are ineligible. This testing is completed because of the possible need for Rescue Therapy if the study treatment is not successful. If the study treatment is not successful, the dentist/periodontist determines the nature and extent of the Rescue Therapy and it may include surgery and/or topical or systemic antibiotics. The risk to any fetus from the study treatment is very low. However, if topical or systemic antibiotics are required because of failure to respond to the study treatment, the risk to the fetus is higher. Hence, pregnancy tests will also be given at visits where additional therapy may be needed, and Arestin will NOT be given if the pregnancy test is positive. In addition, AxiUm, the patient data system in the School of Dental Medicine, will be accessed to identify patients with diabetes who might be eligible, willing and interested in joining the study. For these patients, we will obtain permission of [name] to contact identified patients, if he approves of the selection. Then an IRB-approved letter will be sent to the patients informing them of the study, telling them they may call us for more information or that we may call them to provide information about the study. Patients will also be told

they under no obligation to join the study. From there we will use the IRB-approved Telephone Screen Script and Screening Checklist to provide information to and assess eligibility of patient. All procedures thereafter will be the same as with other participants.

- N/A:** There is no screening as part of this protocol.

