#### 3-MONTH VISIT:

1. Collect the unused Soft-Picks and Paroex® bottle from the participants in the Groups A and B.

2. Ask the subjects to answer the Adverse Event, Taste and Compliance questionnaire.

3. Review medical and dental histories.

4. Taste Test.

5. Oral health examination

6. Collect saliva, subgingival plaque and stool/fecal samples.

6. Anterior teeth cleaning: All subjects will receive anterior teeth cleaning.

7. Groups A and B will have the product, Soft-Picks, replenished and usage instructions reviewed as needed.

8. Make or confirm the next appointment.

9. If any sites where pocket depths stay the same and are  $\geq 5$  mm or if the pockets deepen, periodontal treatment will be repeated.

Exact treatment will be determined by the clinician (dentist or periodontist). The treatment will be explained to the participant and questions will be answered beforehand. Options for Rescue Therapy treatment are:

- Option 1: No additional treatment.
- Option 2: Pocket depths of  $\geq 5$  mm will receive scaling and root planing,
- Option 3: Pocket depths of  $\geq 5$  mm will receive scaling and root planing with the addition of a local antimicrobial agent,

- **Option 4:** Pocket depths of  $\geq 5$  mm will receive modified Widman flap surgery,
- **Option 5:** Pocket depths of  $\geq 5$  mm will receive modified Widman flap surgery with the addition of the GUIDOR® *easy-graft®* CLASSIC Alloplastic Bone Grafting System to infrabony defects that are amenable to regeneration.

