#### **6-MONTH VISIT:**

1. Collect the unused Soft-Picks from the subjects in the Test Group.
2. Ask the subjects to answer the Adverse Event, Taste and Compliance questionnaire.
3. Review medical and dental histories.
4. Taste Test.
5. Oral health examination
6. Collect samples: blood (FBS, HbA1c, Insulin, hs-CRP and microbiome testing, and for future testing of C-peptide, proinsulin, total GLP-1, PYY, DPP-IV, glucagon, LPS, soluble-TNF $\alpha$  RI and RII, MGO, TMAO, creatinine, and for future unknown testing), subgingival plaque, saliva, fecal, skin, and vaginal samples.
7. Retreat all PD  $\geq 5$  mm sites. Subjects will receive additional treatment (Rescue Therapy), including surgery and/or topical or systemic antibiotics, if a clinician (dentist or periodontist) decides they need it. Rescue Therapy is standard of care for non-responsive periodontal lesions, the type depending on the clinical status of the participant. The need for Rescue Therapy (yes, no and type) will be noted in the study records and considered in the analysis of the study data. If on examination, a participant presents with an area showing a clinically defined worsening of their periodontal condition, rescue therapy will be initiated. This therapy will reduce the chance of the tooth being lost from periodontal disease. Rescue therapy will be provided to sites that remain at  $\geq 5$  mm or those demonstrating an increase in pocket depths of  $\geq 2$  mm from the baseline visit bringing them to or above the 5 mm level. Treatment will consist of scaling and root planing of the affected tooth and if the pocket depth is  $\geq 5$  mm, the site may also be treated by local drug delivery with Arestin. In women of childbearing potential, a urine pregnancy test will be provided prior to the placement of Arestin. If the pregnancy test is positive, Arestin will not be used in treatment. Local anesthetic may be used during the procedure as needed. Other treatments for saving the tooth may be given as deemed necessary by the dentist/periodontist clinician, as described above (Number 9 of the 3-

**month Visit).** The clinician will discuss the additional treatment with the participant before it is provided. The clinician providing the rescue therapy in a given subject should not be the clinician that will provide the periodontal measurements for that participant during the study.

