**9-MONTH VISIT:**

**1.** Collect the unused Soft-Picks from the subjects in Groups A and B.

**2.** Ask the subjects to answer the Adverse Event, Taste and Compliance questionnaire.

**3.** Review medical and dental histories.

**4.** Taste Test.

**5.** Oral health examination

**6.** Retreat all PD  $\geq 5$  mm sites. Rescue therapy will be provided to sites that remain at  $\geq 5$  mm or to those demonstrating an increase in pocket depths of  $\geq 2$  mm from the baseline visit bringing them to or above the 5 mm level. Subjects will receive additional treatment (Rescue Therapy), including surgery and/or topical or systemic antibiotics, if a clinician (dentist or periodontist) decides they need it (as described in Number 9 of the 3-month Visit). Again, Rescue Therapy is standard of care for non-responsive periodontal lesions, the type depending on the clinical status of the participant. The need for Rescue Therapy (yes, no and type) will be noted in the study records and considered in the analysis of the study data.

**7.** Groups A and B will have the product, Soft-Picks, replenished and usage instructions reviewed as needed.

**8.** Make or confirm the next appointment.

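### Section 21.4 reports no known fetal risk although Section 8.1 describes one, and the pregnancy-test safeguard in 8.1 is carried into only one of the three rescue visits in 10.1, for Arestin alone

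*Combined protocol and SAP*

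**What the plan says.** **Risk statement.** Section 21.4 asks the investigator to "indicate which research procedures may have risks to an embryo or fetus should the subject be or become pregnant". The entry is "Response: None known". (The same words answer 21.5, on risks to non-participants; the 21.4 answer is the one at issue.)

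Section 8.1 (Eligibility Screening) makes two statements on the same subject. For the assigned treatment: "The risk to any fetus from the study treatment is very low". For rescue: "if topical or systemic antibiotics are required because of failure to respond to the study treatment, the risk to the fetus is higher".

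**Testing and withholding.** Section 8.1 also says that "pregnancy tests will also be given at visits where additional therapy may be needed", and that Arestin is withheld after a positive result.

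**Visit procedures in Section 10.1.**
- 3-month visit, item 9: one rescue option is "scaling and root planing with the addition of a local antimicrobial agent". No pregnancy test is listed.
- 6-month visit, item 7: rescue may include topical or systemic antibiotics. For women of childbearing potential, "a urine pregnancy test will be provided prior to the placement of Arestin", and Arestin is not used if the test is positive.
- 9-month visit, item 6: rescue is allowed, "including surgery and/or topical or systemic antibiotics, if a clinician (dentist or periodontist) decides they need it". No pregnancy test is listed, and the cross-reference is to item 9 of the 3-month visit, which has none either.

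**The concern.** Two things do not match. First, the section of the protocol devoted to fetal risk reports none, while the screening section acknowledges a risk and uses it to justify pregnancy testing. Someone who consults only Section 21 would not learn of it.

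Second, the safeguard has different triggers in different places. In 8.1 the trigger is the visit: any visit at which further therapy may be needed. In the 6-month list it is one product. In the 3- and 9-month lists there is no trigger. Staff following the visit lists could therefore omit a test that 8.1 promises. After a positive test, the protocol gives no instruction for the other agents that 8.1 places in the higher-risk category. What is at stake is participant protection and an accurate risk description, not the efficacy analysis.

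**Working it through.** No formula applies and the plan gives no figure to reproduce. The check sets the current text side by side.

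**Step 1: the risk statement.**

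| Source | Study treatment | Antibiotic rescue |
|---|---|---|
| 21.4 | none known | none known (not mentioned) |
| 8.1 | very low | higher, for topical or systemic agents |

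The gap on study treatment is small. The gap on antibiotic rescue is one of substance. The rest of Section 21 does not close it: the list in 21.1 covers the examination, sample collection, radiographs, Paroex, Soft-Picks and the taste test, but names neither Arestin nor systemic antibiotics nor any other rescue treatment.

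**Step 2: testing at each rescue visit.**

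| Visit | Antimicrobial or antibiotic rescue allowed in 10.1 | Test stated in 10.1 | Test under the 8.1 rule |
|---|---|---|---|
| 3 months | yes, local agent | no | yes |
| 6 months | yes, topical or systemic | only before Arestin | yes |
| 9 months | yes, topical or systemic | no | yes |

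Section 10.1 therefore states a test at 1 of 3 rescue visits, against 3 of 3 under 8.1. Even at month 6 the two differ: a woman given a systemic antibiotic without Arestin falls under the 8.1 testing rule but not under the 6-month wording.

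**Step 3: what a positive test changes.** The withholding rule appears in 8.1 and in the 6-month list, and both name Arestin only. Section 8.1 attributes the higher risk to topical and systemic antibiotics as classes. For systemic antibiotics, and for any local agent other than Arestin, the protocol does not say what follows a positive result.

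**The case against.** The strongest defence of 21.4 is scope. It asks about research procedures, and Section 10.1 describes Rescue Therapy as standard of care, given on a clinician's decision. On that reading rescue lies outside the question. This does not hold. Section 21.1 describes all the study procedures as standard of care and then lists their risks, so that label does not take a procedure out of Section 21. Rescue is also written into the protocol's own visit procedures, and 8.1 gives possible rescue as the reason for pregnancy testing.

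The strongest defence of the safeguards is that 8.1 is a general rule that already reaches months 3 and 9, and no visit list says that testing is unnecessary. That stands, and it limits the point: the visit lists fail to carry the rule through, but they do not cancel it. It does not explain the narrower trigger at month 6 or the Arestin-only withholding rule, which 8.1 itself shares.

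It is also true that pregnancy is an exclusion and is tested for at screening. But participation lasts about 12 to 13 months, and 21.4 expressly covers a participant who becomes pregnant.

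A reader might infer that staff would not test at 3 or 9 months. The documents do not support that. Section 10.4 lists visit checklists, one of them for Rescue Therapy; 10.3 refers to a Manual of Procedures; and 14.4 says staff are trained on the protocol and all SOPs. None of these documents is available here, and any of them may contain the step.

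A reader might also infer that participants are given a wrong risk statement. Section 21.4 is an entry in the protocol, and the consent form was not available for this review, so that is a point to check, not a finding.

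**Conclusion.** The point holds as an internal inconsistency, wrong as written and of modest severity. Section 21.4 cannot stand beside 8.1. The safeguard promised in 8.1 appears at one of three rescue visits in 10.1, with a narrower trigger there. The positive-test rule covers fewer agents than the risk statement that motivates it.

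The number of women affected cannot be estimated from the documents. A reader might take the hypothesised 35% needing rescue (Section 1.2), 0.35 × 104 = 36.4, and apply an assumed 40–60% share of women to get 14.6 to 21.8. That does not measure the problem. The sex split is an assumption. The options in 10.1 include no additional treatment, scaling alone and surgery, so only an unknown part of those needing rescue would receive an antimicrobial. Eligibility starts at age 25 with no upper limit, so the share of childbearing age is also unknown.

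The conclusion rests on the protocol text alone. The primary endpoint, sample size and analysis are not affected.

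**What to change.** Reconcile Section 8.1, Section 21.4 and the 3-, 6- and 9-month lists in Section 10.1 so that they agree on three matters:

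1. one statement of embryo and fetal risk, covering both the study treatment and rescue;
2. the visits, and the trigger at each, at which pregnancy testing applies;
3. the set of rescue agents to which the positive-test rule applies.

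Then check the Rescue Therapy checklist and the consent form against the reconciled text and amend them only if they differ. What the rule should contain is for the investigators and the IRB to decide; the request here is that it be stated once and carried through.

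The cost is an amendment to protocol wording and, if needed, to the checklist and consent form. Section 8.1 already commits the study to testing at visits where further therapy may be needed. Any added procedural burden depends on the rule that the investigators settle on.
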